## 11. Duration of the FFR procedure

## 5. Study Design and Population

This study is designed as a prospective, observational, multi-center, single-arm, clinical registry to estimate the ischemic burden of angiographically intermediate proximal LAD stenosis in clinical practice using the OpSens Medical OptoWire Deux FFR system. Subjects with stable angina or unstable angina who are found to have an intermediate proximal LAD stenosis on coronary angiography with anatomy amenable to PCI and underwent physiological lesion assessment with the OptoWire Deux pressure wire and OCT as part of their routine procedures using standard of care techniques will be enrolled. Patients meeting enrollment criteria will be offered the opportunity to enroll in this observational registry post-procedure. All patients enrolled in this study are expected to be evaluated and treated using a standard of care technique. This study will enroll a total of 60 patients at Columbia University Medical Center and St. Francis Hospital.

### 5.1. Determination of Study Eligibility

Subjects eligible for initial study screening are patients with stable angina, unstable angina or NSTEMI (if the LAD lesion is the non-culprit lesion), who are referred to coronary angiography and have had an invasive FFR measurement and OCT in the LAD artery. Subjects will need to read and sign the required informed consent document and fulfill the necessary eligibility criteria, as described below, to be enrolled in the study.

### 5.2. Inclusion Criteria

1. Male or female subjects, >18 years of age.
2. Patients with stable angina, unstable angina or non-ST segment elevation myocardial infarction (if the LAD lesion is the non-culprit lesion) and in whom an intermediate proximal LAD stenosis (30-80%) with TIMI flow 3 has been identified on angiography.

**NOTE:** Patients with multi-vessel disease can be enrolled.

3. Patients have had FFR and OCT of the LAD with the OpSens FFR system as part of their routine evaluation as standard of care procedure
4. Provides written, informed consent and HIPAA consent to use the data in a clinical study.

### 5.3. Exclusion Criteria

#### *General exclusion criteria*

1. Patients presented with NSTEMI with the LAD involved as the culprit lesion
2. Any ST-elevation myocardial infarction within the past 30 days.
3. Hemodynamic instability requiring vasopressor or mechanical circulatory support.
4. Prior heart transplant.
5. Known left ventricular ejection fraction  $\leq 40\%$ .
6. LAD supplying akinetic or severely hypokinetic territories if already known based on prior imaging.

7. Patient is enrolled in another clinical study that may impact the results of this study.
8. FFR not acquired per the IFU for the OpSens Wire.
9. LAD Lesion not assessed with OCT

*Angiographic exclusion criteria*

1. TIMI grade 2 or lower at baseline angiography.
2. Target lesion involves left main (stenosis  $>50\%$ ).
3. Presence of chronic total occlusion in any vessel.
4. Presence of a side branch  $\geq 2.75$  mm with  $\geq 70\%$  stenosis in the LAD.
5. Bifurcation lesion that resulted in the stent implantation of a side branch.

#### **5.4. Subject Screening and Informed Consent**

At the investigational centers (Columbia University Medical Center and St. Francis Hospital), a qualified Investigator or his designee will approach individual patients who are potential candidates for participation after the patient has fully recovered from the procedure and will explain the purpose, procedures, risks, benefits, and intent of the study to each. Interested subjects will be invited to join the study and asked to provide written informed consent as well as HIPAA consent to use the data for research purposes.

The informed consent form used must be approved by the IRB/EC and other local regulatory bodies (as appropriate). The approved consent form should clearly reflect the IRB/EC approval date.

Failure to obtain a signed and hand-dated informed consent form will preclude enrollment in this registry.

All subjects who begin the study screening process will be tracked by utilizing a study screening log. The screening log documents the screening effort to enroll consecutively eligible subjects in this study.

#### **5.5. Subject Enrollment**

Subjects will be recruited consecutively at Columbia University Medical Center and St. Francis Hospital. This is intended to ensure that the range of FFR values in the sample will represent that of the intended use population. Subjects who fail to meet the clinical inclusion and exclusion criteria will not be included in this study. Subjects will only be formally enrolled in the study after all clinical and angiographic criteria are met and the subject provides informed consent and HIPAA consent.

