### 3. Background

#### 3.1. Fractional flow reserve

Fractional flow reserve (FFR) is an index that quantifies the hemodynamic significance of coronary artery stenosis. FFR is obtained by measuring the ratio between pressure distal to a stenosis and proximally using specialized pressure-measuring guidewires during maximal hyperemia. FFR is considered the standard of reference for clinical decision-making. Clinical outcome studies have shown that medical therapy is preferred for non-hemodynamically significant lesions (FFR >0.80), while coronary revascularization should be considered in cases of significant functional stenosis (FFR ≤0.80). Society guidelines reflect the importance of physiology-guided revascularization, with the ACCF/AHA/SCAI guidelines recommending that FFR is used to guide the treatment strategy in stable coronary lesions. Furthermore, the most recent appropriate use criteria advocates for expanded use of intracoronary physiologic testing.

Nevertheless, for a variety of practical reasons, FFR measurements remain underutilized. Conventional pressure guidewires are limited by three main factors. First, pressure-measuring guidewires have a more complex design than standard guidewires used in percutaneous coronary interventions (PCI). Consequently, traditional pressure guidewires have handling, torquability and lesion crossing characteristics that are suboptimal compared to the mechanical performance of workhorse guidewires. In the FFR cohort in the DEFINE-FLAIR study, only 30.7% of PCI procedures were performed with a pressure wire. A pressure wire with improved handling characteristics to permit use as a workhorse guidewire during interventions fills an important void and improves the likelihood an operator assesses post-intervention FFR by avoiding the need to cross with an additional wire.

Secondly, pressure drift can lead to unreliable FFR values and is a prominent limitation with conventional pressure wires. Drift can occur when air bubbles become trapped in the cavity of the pressure sensor coupled with the inherent thermal and electrical instability of pressure sensors. Signal drift has been reported to occur in as many as 17.5% of FFR cases. Lastly, contrast agents and blood can affect connectivity with conventional pressure wires, reducing its reliability post-stenting.

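### Does consecutive recruitment (Section 5.5) claim more representativeness than a registry limited to patients with both OptoWire FFR and OCT can deliver?

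*Combined protocol and SAP*

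**What the plan says.** Section 5.5 recruits consecutively at two sites and gives the reason: "This is intended to ensure that the range of FFR values in the sample will represent that of the intended use population". The documents do not define that population.

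The eligibility text sets who can be in the series:

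- Section 5.1 opens screening to patients who "have had an invasive FFR measurement and OCT in the LAD artery".
- Section 5.2, inclusion 3: "Patients have had FFR and OCT of the LAD with the OpSens FFR system as part of their routine evaluation".
- Section 5.3, general exclusions 8 and 9: "FFR not acquired per the IFU for the OpSens Wire" and "LAD Lesion not assessed with OCT".
- Section 5.3, angiographic exclusion 5: "Bifurcation lesion that resulted in the stent implantation of a side branch".
- Section 5.4 seeks consent after recovery from the procedure, and "Failure to obtain a signed and hand-dated informed consent form will preclude enrollment in this registry".

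Endpoints 1 and 2 (Sections 1 and 4.3) are the rates of FFR ≤0.80 and of resting Pd/Pa ≤0.92 in intermediate proximal LAD lesions. Sections 5 and 8 describe the study as estimating the ischemic burden of such stenoses. None of these sentences repeats the OptoWire-plus-OCT condition.

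**The concern.** Consecutive recruitment prevents picking and choosing within the group being recruited. It cannot correct for how that group came about. Here the group consists of patients whose operators had already chosen both tests, whose FFR was acquired per the instructions for use, who did not receive a side-branch stent, and who later consented.

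If any of these steps depends on FFR, the share of positive lesions among the 60 enrolled will differ from the share among intermediate proximal LAD lesions at large. One step has a route to FFR in the documents. Exclusion 5 depends on stenting, and Section 3.1 says that "coronary revascularization should be considered in cases of significant functional stenosis", with FFR ≤0.80 as the threshold.

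At stake is how far two secondary rates and the ischemic-burden statement can be generalised. The documents do not show that the primary drift endpoint is affected.

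**Working it through.** **Step 1. Compare the claim with the sampled group.** Section 5.5 states an intention. It speaks of the range of FFR values, not of rates, and it refers to an undefined intended use population. Section 3.3 describes the wire's approved use as pressure measurement during diagnostic angiography and coronary interventions. If the intended use population means patients in whom the wire is used, OptoWire use helps to define that population, and only OCT, acquisition per the instructions, the other exclusions and consent narrow it.

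In Section 5, the sentence directly after the ischemic-burden aim restricts subjects to those assessed with the OptoWire and OCT in routine care. The Subject Population row in Section 1 and Section 6.3 do the same. A reader of endpoints 1 and 2 therefore has the restriction in view.

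**Step 2. Inputs for an illustration.** The documents give n = 60. They give no expected FFR-positive rate, OCT uptake or side-branch stenting rate, so the following are assumptions:

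- π, the true FFR-positive share: 30%, 40% or 50%.
- s, the chance that an FFR-positive lesion enters divided by the chance that an FFR-negative lesion enters. It can stand for any one filter or for all of them together; s = 1 means no bias.
- All 60 patients are evaluable, and the yardstick is an exact (Clopper-Pearson) 95% interval. Section 8.2 mentions 95% intervals only for baseline and procedural variables.

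**Step 3. Expected enrolled rate.** Rate = πs / (πs + 1 − π). At π = 0.40:

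| s | Calculation | Expected rate |
|---|---|---|
| 0.5 | 0.20 / 0.80 | 25.0% |
| 0.8 | 0.32 / 0.92 | 34.8% |
| 1 | 0.40 / 1.00 | 40.0% |
| 1.25 | 0.50 / 1.10 | 45.5% |
| 2 | 0.80 / 1.40 | 57.1% |

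**Step 4. How strong must selection be to exceed sampling error?** Solving for s gives s = p(1 − π) / [π(1 − p)], with p set to each interval limit:

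| True rate | Count | Exact 95% interval | Break-even s |
|---|---|---|---|
| 30% | 18/60 | 18.9% to 43.2% | 0.54 and 1.78 |
| 40% | 24/60 | 27.6% to 53.5% | 0.57 and 1.72 |
| 50% | 30/60 | 36.8% to 63.2% | 0.58 and 1.72 |

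For the 40% row, the lower value is 0.2756 × 0.6 / (0.4 × 0.7244) = 0.571 and the upper is 0.5346 × 0.6 / (0.4 × 0.4654) = 1.723.

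**Step 5. Exclusion 5 alone.** Take the least favourable case: it removes a share q of FFR-positive lesions and no FFR-negative ones. Then rate = π(1 − q) / (1 − πq). At π = 0.40:

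- q = 5%: 0.38 / 0.98 = 38.8%.
- q = 10%: 0.36 / 0.96 = 37.5%.
- q = 20%: 0.32 / 0.92 = 34.8%.

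All three lie inside 27.6% to 53.5%. Since s = 1 − q here, the rate leaves the interval only when q exceeds 1 − 0.571, about 43% of FFR-positive lesions.

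**The case for a change.** The strongest case for editing the plan is that it costs almost nothing. Stating who is enrolled is not the same as limiting what the estimate applies to, and Section 5.5 leans the other way by presenting consecutive recruitment as the route to representativeness. A confidence interval does not cover selection bias, which would not shrink with more patients, so staying inside the interval does not show that bias is absent. The screening log is unlikely to settle the matter: it tracks those who begin screening, and Section 5.1 confines initial screening to patients who had FFR and OCT.

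Much of this stands. The endpoint wording is broader than the sample, the plan includes no comparison with lesions that lacked one of the tests, and strong selection (s of 0.5 or 2) would matter.

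What does not follow is a need for change. No sentence claims that the results extend to lesions without both tests. The OCT filter has no documented link to FFR. The link through exclusion 5 is thin: Section 3.1 says only that revascularization should be considered, and angiographic exclusion 4 already removes patients with a large, tightly narrowed LAD side branch.

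Adding an OptoWire-and-OCT qualifier to the endpoints would leave out exclusion 5, the one filter with a documented route to FFR. Logging OptoWire cases without OCT would mean recording FFR results of patients who have not consented, which needs IRB agreement. It would still say nothing about lesions never measured with the wire.

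**Conclusion.** The observation is accurate, but no change to the plan follows. Consecutive recruitment secures representativeness only within eligible, consenting patients who had both tests, and the protocol makes that group plain in several places. Requiring OCT is a fair trade-off, because endpoints 4 to 7 cannot be assessed without it. Endpoints 1 and 2 are descriptive secondary rates; no hypothesis test, threshold or decision depends on them. An analyst reporting them would describe the enrolled group and its eligibility criteria as a matter of course, which supplies the limit that the endpoint wording omits.

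The size and direction of any bias are unknown. Under the assumptions above (true rate 30% to 50%, 60 evaluable patients), the expected rate leaves the exact interval only if FFR-positive lesions enter less than about 0.54 to 0.58 times, or more than about 1.72 to 1.78 times, as often as FFR-negative ones. The documents give no sign of selection that strong, and they do not rule it out.

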#### **5.6. Subject Withdrawal**

Subjects have the right to withdraw from the study at any time and for any reason without prejudice to their future medical care by the study personnel or institution.

## 6. Procedures and Assessments

### 6.1. Schedule of Events

**Table 1: Schedule of Events**

Study Requirement	Post-procedure
Informed consent and HIPAA consent to use data	X
Demographics	X
Medical history and baseline medication	X
Collection of procedural information	X

### 6.2. Baseline Procedures

The following data must be collected for all patients post-procedure, unless otherwise specified:

- ◆ Subject demographics
- ◆ Medical history
- ◆ Baseline medications
- ◆ Clinical assessment
- ◆ Procedural information

### 6.3. Procedural Protocol

In patients with an angiographically intermediate proximal LAD lesion, eligible for enrollment in the study whom an OptoWire Deux was used for physiologic lesion assessment in addition to OCT as standard of care, will be offered consent for enrolling in this observational study post-procedure.

### 6.4. Procedural Information

The following procedural information will be collected:

- ◆ Number of OptoWire Deux used
- ◆ Number of workhorse wires used
- ◆ Total duration of procedure
- ◆ Duration of FFR measurement
- ◆ Coronary angiogram (DICOM)
- ◆ OCT images
- ◆ Cine marking the position of the FFR wire pressure sensor (DICOM)
- ◆ Physiology tracing (resting Pd/Pa, FFR, pullback)

### 6.5. Shipment of Materials to the Core Lab

The following documentation should be forwarded to the Core Lab:

- ◆ Coronary angiogram (saved on a CD labeled with patient ID)
- ◆ FFR tracings
- ◆ OCT images
- ◆ Study worksheet (Appendix B)
- ◆ Catheterization report

Cardiovascular Research Foundation Core Lab

Trial Identifier: OpSens FFR Trial  
[name]  
[name]  
USA

## 7. Study Risk Determination

Participation in this study presents no medical risk to the patient (data collection only).

## 8. Statistical Considerations

This is a prospective, observational, multi-center, clinical study designed to estimate the ischemic burden of angiographically intermediate proximal LAD stenosis using FFR. Efficacy will be measured using the OpSens FFR system.

The study's primary endpoint is the rate of significant drift, defined as FFR <0.97 or >1.03 with the pre-PCI FFR recording using the OpSens OptoWire Deux pressure wire system.

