## 1. Protocol Summary

Study Title	The Drift-Reduction for Improved FFR using Fiberoptic Technology (DRIFT) study
Device Description	OpSens Medical OptoWire Duex Pressure Wire
Study Design	Prospective, observational, multi-center, single-arm, clinical registry
Objectives	The primary objective of this study is to assess the accuracy, efficacy and durability of the OpSens Medical OptoWire Deux Pressure Wire in the assessment of angiographically intermediate proximal left anterior descending (LAD) stenosis in clinical practice.
Subject Population	Subjects with stable angina, unstable angina, or non-ST segment elevation myocardial infarction (if the LAD lesion is the non-culprit lesion) who are referred to coronary angiography and have an angiographically intermediate proximal LAD stenosis with anatomy amenable to percutaneous intervention. Patients meeting enrollment criteria and had fractional flow reserve (FFR) with the OpSens FFR system and optical coherence tomography (OCT) of the LAD as part of their routine care using a standard of care technique will be eligible for enrollment in this study.
Number of Subjects and Sites	This study will enroll a total of 60 patients at Columbia University Medical Center and St. Francis Hospital.
Primary Endpoint	The primary endpoint is the rate of significant drift, defined as $Pd/Pa < 0.97$ or $> 1.03$ in the pre-percutaneous coronary intervention (PCI) FFR recording.
Secondary Endpoint	
Secondary efficacy endpoints:
 
 
1. The rate of pre-PCI positive FFR (<math>\leq 0.80</math>) in angiographically intermediate proximal LAD lesions.
 
2. The rate of pre-PCI resting <math>Pd/Pa</math> (<math>\leq 0.92</math>) in angiographically intermediate proximal LAD lesions.
 
3. The rate of significant drift defined as <math>Pd/Pa < 0.97</math> or <math>> 1.03</math> with post-PCI FFR recording.
 
4. Pre-PCI OCT correlation (minimum lumen area [MLA] <math>< 2.5 \text{ mm}^2</math>) with FFR (<math>\leq 0.80</math>).
 
5. Pre-PCI OCT correlation with the pullback for distinguishing focal (step-up <math>\geq 0.03</math>) versus diffuse disease defined by pre-PCI resting <math>Pd/Pa</math> pullback.
 
6. Post-PCI OCT correlation (edge dissection [lumen area within the dissection <math>< 4.5 \text{ mm}^2</math>], stent underexpansion [<math>< 4.5 \text{ mm}^2</math>]).
 

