### 4.3. Secondary Endpoints

*Secondary efficacy endpoints:*

1. The rate of pre-PCI positive FFR ( $\leq 0.80$ ) in angiographically intermediate proximal LAD lesions.
2. The rate of pre-PCI resting  $Pd/Pa$  ( $\leq 0.92$ ) in angiographically intermediate proximal LAD lesions.
3. The rate of significant drift defined as  $Pd/Pa < 0.97$  or  $> 1.03$  with post-PCI FFR recording.
4. Pre-PCI OCT correlation (MLA  $< 2.5 \text{ mm}^2$ ) with FFR ( $\leq 0.80$ ).
5. Pre-PCI OCT correlation with the pullback for distinguishing focal (step-up  $\geq 0.03$ ) versus diffuse disease defined by pre-PCI resting  $Pd/Pa$  pullback.
6. Post-PCI OCT correlation (edge dissection [lumen area within the dissection  $\leq 4.5 \text{ mm}^2$ ], stent underexpansion [ $\leq 4.5 \text{ mm}^2$  in 3-mm vessel or  $\leq$  distal reference lumen area], residual disease outside of stent [minimum lumen area  $< 4.5 \text{ mm}^2$ ]) with the pullback for distinguishing focal (step-up  $\geq 0.03$ ) versus diffuse disease defined by post-PCI resting  $Pd/Pa$  pullback.
7. The rate of discrepancy between FFR and resting physiology indices and its correlation with an OCT derived MLA.

*Secondary economic endpoints:*

8. Total number of OptoWires used during the procedure.
9. Frequency of use of alternative guidewire (workhorse wire) for the procedure.
10. Total duration of the procedure

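### Section 8 puts the drift limits of the primary endpoint on FFR, whereas Sections 1 and 4.2 put them on Pd/Pa; taken literally, Section 8 counts diseased lesions as sensor drift

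*Combined protocol and SAP*

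**What the plan says.** The primary endpoint is defined in three places.

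- Section 1 (Protocol Summary): "rate of significant drift, defined as $Pd/Pa < 0.97$ or $> 1.03$ in the pre-percutaneous coronary intervention (PCI) FFR recording".
- Section 4.2 (Primary Endpoint): the same Pd/Pa limits, again for the pre-PCI recording.
- Section 8 (Statistical Considerations): "primary endpoint is the rate of significant drift, defined as FFR <0.97 or >1.03 with the pre-PCI FFR recording".

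Secondary endpoint 3 in Section 4.3 is the post-PCI counterpart. It also places the limits 0.97 and 1.03 on Pd/Pa, "with post-PCI FFR recording".

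Secondary endpoint 1 in the same section is "The rate of pre-PCI positive FFR", with positive meaning 0.80 or below. Section 3.1 describes how FFR is obtained: "measuring the ratio between pressure distal to a stenosis and proximally using specialized pressure-measuring guidewires during maximal hyperemia". On drift, the same section says: "Drift can occur when air bubbles become trapped in the cavity of the pressure sensor", and adds thermal and electrical instability of the sensor as causes. Section 6.4 lists resting Pd/Pa, FFR and pullback as separate parts of the physiology tracing. Section 9 (Definitions) covers reference vessel diameter and TIMI flow but not drift.

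**The concern.** As this protocol uses the terms, FFR and drift are different things. FFR measures how much a lesion limits flow, while drift is an error of the pressure sensor. Putting the drift limits on FFR therefore changes what the primary endpoint measures.

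Section 8 is the only statistical section, so it is the natural source for programming the primary analysis. Its opening describes the study as estimating ischemic burden by FFR, so nothing there alerts the reader that FFR is the wrong variable in the next sentence. The tracings will yield a value labelled FFR for each patient, so the literal definition can be programmed without raising an error.

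If that happened, the headline result would describe the lesions enrolled and not the wire. It also could not be read against the background statement that motivates the study: "Signal drift has been reported to occur in as many as 17.5% of FFR cases".

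**Working it through.** The plan gives no figure that depends on this definition, so there is none to reproduce. The check compares the definitions and then works out what the literal Section 8 reading implies.

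**Definitions side by side**

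| Place | Recording | Variable | Limits |
|---|---|---|---|
| Section 1 | pre-PCI | Pd/Pa | <0.97 or >1.03 |
| Section 4.2 | pre-PCI | Pd/Pa | <0.97 or >1.03 |
| Section 4.3, item 3 | post-PCI | Pd/Pa | <0.97 or >1.03 |
| Section 8 | pre-PCI | FFR | <0.97 or >1.03 |

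Only Section 8 differs, and only in the variable.

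**Inputs:** N = 60 (Sections 1 and 5); positive FFR ≤0.80 (Section 4.3, item 1); drift limits 0.97 and 1.03 (Section 8); background drift of up to 17.5% (Section 3.1). Assumption: all 60 patients are evaluable, each with one pre-PCI FFR.

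**Step 1: overlap with secondary endpoint 1.** FFR ≤0.80 lies wholly inside FFR <0.97, with a margin of 0.97 − 0.80 = 0.17. Hence

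Section 8 rate = rate(FFR ≤0.80) + rate(0.80 < FFR < 0.97) + rate(FFR >1.03) ≥ rate(FFR ≤0.80).

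This holds for any distribution of FFR. Each positive FFR adds 1/60 = 1.7 percentage points to the supposed drift rate.

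**Step 2: scale against 17.5%.** 0.175 × 60 = 10.5 patients. Since 10/60 = 16.7% and 11/60 = 18.3%, at most 10 patients could lie outside 0.97-1.03 if the rate is not to exceed 17.5%. The other 60 − 10 = 50 would need an FFR from 0.97 to 1.03. Yet patients are enrolled because "an intermediate proximal LAD stenosis (30-80%) with TIMI flow 3 has been identified on angiography".

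**Step 3: illustration only.** The documents give no FFR distribution. If FFR is assumed normal with mean 0.78 to 0.90 and SD 0.06 to 0.10, P(FFR <0.97) + P(FFR >1.03) runs from 85.5% (mean 0.90, SD 0.10; 51.3 of 60) to 99.9% (mean 0.78, SD 0.06; 60.0 of 60). The conclusion does not rest on these assumed values.

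**The case against.** The best case against is that nobody would be misled. Section 8 names the quantity as drift, Section 3.1 explains drift as a sensor fault, the limits lie symmetrically 0.03 either side of 1.00, and both other statements of the endpoint say Pd/Pa. Tracings also go to a core laboratory. To produce the absurd rate, an analyst would have to ignore all of this. Much of that is fair: the wording is probably a slip and the intent can be recovered. But someone programming from the statistical section should not have to overrule it to get the primary endpoint right.

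A sharper version is that FFR is itself a Pd/Pa ratio. Sections 1 and 4.2 leave Pd/Pa unqualified, so read equally literally they could mean the hyperemic value beyond the lesion. If context rescues those sections, it should rescue Section 8 too. This does not succeed as a defence. Unqualified Pd/Pa leaves room for the sensor-check reading, whereas FFR, as Section 3.1 describes it, does not. The argument does expose a real gap: the definitions name the recording but not the sensor position or the moment at which drift is read. A Pd/Pa read beyond the lesion would overlap with the protocol's own lesion criteria (resting Pd/Pa ≤0.92 in Section 3.2.3, step-up ≥0.03 in Section 3.2.4). The instructions for use, cited in the exclusion criteria, or the Appendix B worksheet may settle this; neither was available.

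Two limits also stand. The absence of a precedence rule is established only for the available text, which lacks Section 2 as well as those two items. And the plan schedules no formal comparison with 17.5%, nor does it give the drift definition behind that figure, so it serves here only as a scale.

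**Conclusion.** The concern holds and must be fixed. The statistical section names the wrong variable for the primary endpoint and contradicts the two other statements of that endpoint.

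Applied literally, it makes the primary rate at least as large as the positive-FFR rate, whatever the FFR distribution, provided both use the same denominator. With 60 evaluable patients, the rate stays at or below 17.5% only if 50 or more have an FFR from 0.97 to 1.03. The consequence is confined to the reported primary rate, because the analysis is descriptive and no test or error rate is involved. The severity rests on the contradiction alone and not on the gap about where and when Pd/Pa is read.

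**What to change.** In Section 8, replace the FFR limits with the Pd/Pa definition from Sections 1 and 4.2. Those sections and secondary endpoint 3 already agree, so nothing else needs to change to remove the contradiction.

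Then check the instructions for use and the Appendix B worksheet. Only if neither says where and when drift is read, add a phrase to the endpoint definition stating that Pd/Pa is taken where no gradient across the lesion is expected, in line with the instructions for use.

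The cost is one text substitution and possibly one added phrase. No new data or patient procedure is needed: Section 6.4 already collects the tracings and a cine of the sensor position.
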